### 11.2 Appendix 2 - Criteria for Potentially Clinically Significant Abnormalities (PCSA)

Vital signs		
PR	$\leq 50$ bpm	$\geq 120$ bpm
SBP	$\leq 90$ mmHg	$> 140$ mmHg
DBP	$\leq 50$ mmHg	$> 90$ mmHg
ECG parameters		
PR	$< 120$ ms	$> 200$ ms
QRS		$> 120$ ms
QTcB or QTcF		$> 450 - \leq 480$ ms $> 480$ ms $> 500$ ms change from baseline $\geq 30 - \leq 60$ ms change from baseline $> 60$ ms

## 11.3 Appendix 3 - List of tables, listings and figures included in the clinical study report

NUMBER	TITLE
14	Tables, figures and graphs referred to but not included in the text
14.1	Demographic data
14.1.1	Description of study subjects
14.1.1.1	Subjects disposition - Included set
14.1.1.2	Analysis sets – Included set
14.1.2	Protocol deviations
14.1.2.1	Deviations relating to inclusion/exclusion criteria - Safety set
14.1.2.2	Other deviations - Safety set
14.1.3	Demographic data and baseline characteristics
14.1.3.1.1	Demographic data - Safety set
14.1.3.1.2	Demographic data - PKS
14.1.3.2	Other baseline characteristics
14.1.3.2.1.1	HCV genotype – Safety set
14.1.3.2.1.2	HCV genotype – PKS
14.1.3.2.2.1	HCV RNA – Safety set
14.1.3.2.2.2	HCV RNA – PKS
14.1.3.2.3.1	Serology - Safety set
14.1.3.2.3.2	Serology - PKS
14.1.3.2.4	Listing of positive results of serology - Safety set
14.1.3.2.5.1	Cirrhosis status - Safety set
14.1.3.2.5.2	Cirrhosis status - PKS set
14.1.3.2.6.1	Liver biopsy – Safety set

14.1.3.2.6.2	Liver biopsy – PKS
14.1.3.2.7.1	Fibroscan - Safety set
14.1.3.2.7.2	Fibroscan - PKS set
14.1.3.3	Medical and surgical history
14.1.3.3.1	Previous medical and surgical history (except liver diseases) - Safety set
14.1.3.3.2	Ongoing medical and surgical history (except liver diseases) - Safety set
14.1.3.3.3	Previous liver diseases - Safety set
14.1.3.3.4	Ongoing liver diseases - Safety set
14.1.3.4	Previous and concomitant medications
14.1.3.4.1	Previous medications - Safety set
14.1.3.4.2	Concomitant medications - Safety set
14.2	Pharmacokinetic data
14.2.1	Plasma concentrations
14.2.1.1	AL-335, ALS-022399 and ALS-022227
14.2.1.1.1	Plasma concentrations for AL-335, ALS-022399 and ALS-022227 - Pharmacokinetic set
14.2.1.1.2	Graphs of plasma concentrations means ( $\pm$ SD) over time for AL-335, ALS-022399 and ALS-022227 - Pharmacokinetic set
14.2.1.1.2.1	Graphs of plasma concentrations means ( $\pm$ SD) over time for AL-335, ALS-022399 and ALS-022227 by analyte
14.2.1.1.2.2	Graphs of plasma concentrations means ( $\pm$ SD) over time for AL-335, ALS-022399 and ALS-022227 by cohort
14.2.1.1.3	Graphs of trough plasma concentrations means ( $\pm$ SD) over time for AL-335, ALS-022399 and ALS-022227 - Pharmacokinetic set

14.2.1.2	Simeprevir
14.2.1.2.1	Plasma concentrations for simeprevir - Pharmacokinetic set
14.2.1.2.2	Graphs of plasma concentrations means ( $\pm$ SD) over time for simeprevir - Pharmacokinetic set
14.2.1.2.3	Graphs of trough plasma concentrations means ( $\pm$ SD) over time for simeprevir - Pharmacokinetic set
14.2.1.3	Odalasvir
14.2.1.3.1	Plasma concentrations for odalasvir - Pharmacokinetic set
14.2.1.3.2	Graphs of plasma concentrations means ( $\pm$ SD) over time for odalasvir - Pharmacokinetic set
14.2.1.3.3	Graphs of trough plasma concentrations means ( $\pm$ SD) over time for odalasvir - Pharmacokinetic set
14.2.2	PK parameters in plasma
14.2.2.1	AL-335, ALS-022399 and ALS-022227
14.2.2.1.1	PK parameters in plasma for AL-335, ALS-022399 and ALS-022227 - Pharmacokinetic set
14.2.2.1.2	Scatter plots of $C_{max}$ and $AUC_{0-\tau}$ for AL-335, ALS-022399 and ALS-022227 by cohort - Pharmacokinetic set
14.2.2.1.3	Box whisker plots of $C_{max}$ and $AUC_{0-\tau}$ for AL-335, ALS-022399 and ALS-022227 by cohort - Pharmacokinetic set
14.2.2.2	Simeprevir
14.2.2.2.1	PK parameters in plasma for simeprevir - Pharmacokinetic set
14.2.2.2.2	Scatter plots of $C_{max}$ and $AUC_{0-\tau}$ for simeprevir by cohort - Pharmacokinetic set
14.2.2.2.3	Box whisker plots of $C_{max}$ and $AUC_{0-\tau}$ for simeprevir by cohort - Pharmacokinetic set
14.2.2.3	Odalasvir

14.2.2.3.1	PK parameters in plasma for odalasvir - Pharmacokinetic set
14.2.2.3.2	Scatter plots of $C_{max}$ and $AUC_{0-\tau}$ for odalasvir by cohort - Pharmacokinetic set
14.2.2.3.3	Box whisker plots of $C_{max}$ and $AUC_{0-\tau}$ for odalasvir by cohort - Pharmacokinetic set
14.3	Safety data
14.3.1	Adverse events
14.3.1.1	Adverse events - Safety set
14.3.1.2	Treatment emergent adverse events
14.3.1.2.1	Treatment emergent adverse events summary table - Safety set
14.3.1.2.2	Treatment emergent adverse events - Safety set
14.3.1.2.3	Treatment emergent adverse events by preferred term - Safety set
14.3.1.2.4	Treatment emergent adverse events by intensity - Safety set
14.3.1.2.5	Treatment emergent adverse events by causality - Safety set
14.3.1.2.6	Treatment emergent serious adverse events by preferred term - Safety set
14.3.1.2.7	Treatment emergent adverse events leading to any study drug discontinuation by preferred term - Safety set
14.3.1.2.8	Treatment emergent adverse events of special interest - Safety set
14.3.1.2.9	Adverse Events with fatal outcome – Included set
14.3.1.2.10	The incidence and comparable prevalence rate per 2-week time interval for any AEs
14.3.1.2.11	The incidence rates for adverse events of special interest by WHO toxicity grade
14.3.1.2.12	The incidence rates for adverse events of special interest by relationship to study drugs

14.3.1.2.13	The incidence rates for serious adverse events of special interest by relationship to study drugs
14.3.1.2.14	Time to the first occurrence of adverse events of special interest
14.3.1.2.15	The incidence and comparable prevalence rate per 2-week time interval for adverse events of special interest
14.3.1.3.1	Graph of incidence and comparable prevalence rate for any AE over time
14.3.1.3.2	Kaplan Meier Curve for the Time to Onset of adverse events of special interest
14.3.1.3.3	Graph of incidence and comparable prevalence rate for adverse event of special interest over time
14.3.1.3.4	Bar chart of the worst toxicity grade of cardiac events over time
14.3.2.1	Listing of deaths, SAEs and TEAEs leading to study drug discontinuation - Safety set
14.3.2.2	Listing of TEAEs with grade 3 or grade 4 - Safety set
14.3.2.3	Glossary of adverse events
14.3.2.4	Listing of adverse events for subjects who met the study stopping rules
14.3.3	Clinical laboratory data
14.3.3.1	Haematology
14.3.3.1.1	Haematology parameters - Safety set
14.3.3.1.2	Number and percentage of subjects by treatment emergent toxicity grade (Grade 1,2,3,4,3+4) – Worst post-baseline value - Safety set
14.3.3.1.3	Number and percentage of subjects by treatment emergent toxicity grade (Grade 1,2,3,4,3+4) – By measurement time - Safety set
14.3.3.1.4	Listing of all values for subjects presenting any treatment emergent value that is grade 3 and 4 (toxicity grading scale) - Safety set
14.3.3.1.5	Listing of subjects with treatment emergent abnormal values -

	Safety set
14.3.3.1.6	Graphs of individual subject values (spaghetti plots) – Safety Set
14.3.3.1.7	Cross-tabulation of the worst toxicity grades versus baseline
14.3.3.1.8	Plot of mean(SE) by cohort over time
14.3.3.1.9	Plot of mean(SE) change from baseline by cohort over time
14.3.3.1.10	Bar chart of the treatment emergent abnormality by toxicity grade over time
14.3.3.2	Blood chemistry
14.3.3.2.1	Blood chemistry parameters - Safety set
14.3.3.2.2	Number and percentage of subjects by treatment emergent toxicity grade (Grade 1,2,3,4,3+4) – Worst post-baseline value - Safety set
14.3.3.2.3	Number and percentage of subjects by treatment emergent toxicity grade (Grade 1,2,3,4,3+4) – By measurement time - Safety set
14.3.3.2.4	Listing of all values for subjects presenting any treatment emergent values that are grade 3 and 4 (toxicity grading scale) - Safety set
14.3.3.2.5	Listing of subjects with treatment emergent abnormal values - Safety set
14.3.3.2.6	Graphs of individual subject values (spaghetti plots) – Safety Set
14.3.3.2.7	Cross-tabulation of the worst toxicity grades versus baseline
14.3.3.2.8	Plot of mean(SE) by cohort over time
14.3.3.2.9	Plot of mean(SE) change from baseline by cohort over time
14.3.3.2.10	Bar chart of the treatment emergent abnormality by toxicity grade over time
14.3.3.3	Coagulation - Safety set
14.3.3.3.1	Coagulation parameters - Safety set
14.3.3.3.2	Number and percentage of subjects by treatment emergent toxicity grade (Grade 1,2,3,4,3+4) – Worst post-baseline value - Safety set

14.3.3.3.3	Number and percentage of subjects by treatment emergent toxicity grade (Grade 1,2,3,4,3+4) – By measurement time - Safety set
14.3.3.3.4	Listing of all values for subjects presenting any treatment emergent values that are grade 3 and 4 (toxicity grading scale) - Safety set
14.3.3.3.5	Listing of subjects with treatment emergent abnormal values - Safety set
14.3.3.3.6	Cross-tabulation of the worst toxicity grades versus baseline
14.3.3.3.7	Plot of mean(SE) by cohort over time
14.3.3.3.8	Plot of mean(SE) change from baseline by cohort over time
14.3.3.3.9	Bar chart of the treatment emergent abnormality by toxicity grade over time
14.3.3.4	Urinalysis - Safety set
14.3.3.4.1	Urinalysis parameters - Safety set
14.3.3.4.2	Number and percentage of subjects by treatment emergent toxicity grade (Grade 1,2,3,4,3+4) – Worst post-baseline value - Safety set
14.3.3.4.3	Number and percentage of subjects by treatment emergent toxicity grade (Grade 1,2,3,4,3+4) – By measurement time - Safety set
14.3.3.4.4	Listing of all values for subjects presenting any treatment emergent values that are grade 3 and 4 (toxicity grading scale) - Safety set
14.3.3.4.5	Listing of subjects with treatment emergent abnormal values - Safety set
14.3.4	Other safety parameters
14.3.4.1	Vital signs data
14.3.4.1.1	Vital signs parameters - Safety set
14.3.4.1.2	Number and percentage of subjects presenting PCSA values - Safety set
14.3.4.1.3	Listing of subjects presenting PCSA values - Safety set

14.3.4.1.4	Number and percentage of subjects presenting abnormal values – Worst post-baseline value - Safety set
14.3.4.1.5	Number and percentage of subjects presenting abnormal values – By measurement time - Safety set
14.3.4.1.6	Listing of subjects presenting abnormal values - Safety set
14.3.4.1.7	Plots of mean (SE) by cohort over time
14.3.4.2	Electrocardiogram data
14.3.4.2.1	ECG parameters – Safety set
14.3.4.2.2	Number and percentage of subjects with PCSA values - Safety set
14.3.4.2.3	Listing of subjects presenting PCSA values - Safety set
14.3.4.2.4	Listing of All ECG Parameters over time for Subjects with Any Post-baseline Overall Statement of Potentially Clinically Significant Abnormal ECG
14.3.4.2.5	Listing of Subjects with Potentially Progressive PR Prolongation
14.3.4.2.6	Number and percentage of subjects presenting abnormal values – Worst post-baseline value - Safety set
14.3.4.2.7	Number and percentage of subjects presenting abnormal values – By measurement time - Safety set
14.3.4.2.8	Listing of subjects presenting abnormal values - Safety set
14.3.4.2.9	Graphs of individual subject values (spaghetti plots) – Safety Set
14.3.4.2.10	Cross-Tabulation of the worst ECG abnormalities in actual value versus the baseline value
14.3.4.2.11	Cross-Tabulation of the worst QTc increase versus the abnormality on the actual value
14.3.4.2.12	Plots of actual mean(SE) by cohort over time
14.3.4.2.13	Plots of mean change from baseline(SE) by cohort over time
14.3.4.2.14	Spaghetti plot of PR for the patients who had prolonged PR interval

	or AV block (grade $\geq$ 1)
14.3.4.3	Echocardiogram data
14.3.4.3.1	Summary Table of Maximum Decrease from baseline in Mean Ejection Fraction – Safety set
14.3.4.3.2	Number and Percentage of subjects who have a decrease greater than 5% or $\leq$ 10% and $>$ 10% compared to baseline – Safety set
14.3.4.3.3	Listing of all EF values for Subjects with any $>$ 5%- $\leq$ 10 Decrease from baseline in Mean Ejection Fraction – Safety set
14.3.4.3.4	Listing of all EF values for Subjects with any More Than 10% Decrease from baseline in Mean Ejection Fraction – Safety set
14.3.4.3.5	Listing of Ejection Fraction Data and Overall Comment – Safety set
14.3.4.3.6	Echocardiogram parameters – Safety set
14.3.4.3.7	Number and percentage of subjects with abnormal values - Safety set
14.3.4.3.8	Graphs of individual subject values (spaghetti plots) – Safety set
14.3.4.3.9	Plots of actual mean(SE) by cohort over time
14.3.4.3.10	Plots of mean change from baseline(SE) by cohort over time
14.3.4.4	Weight and BMI – Safety set
14.3.4.5	Physical examination
14.3.4.5.1	Physical examination - Safety set
14.3.4.5.2	Abnormal physical examination - Safety set
14.3.4.6	Positive pregnancy test - Safety set
14.4	Efficacy data
14.4.1	HCV RNA – Safety set
14.4.2	Number and percentage of subjects who are HCV RNA not detected or below the limit of quantification – Safety set

14.4.3	Sustained virologic response
14.4.3.1	Number and percentage of subjects with sustained virologic response 12 weeks after end of treatment – Safety set
14.4.3.2	Number and percentage of subjects with sustained virologic response 4 weeks after end of treatment – Safety set
14.4.3.3	Number and percentage of subjects with sustained virologic response 24 weeks after end of treatment – Safety set
14.4.4	Number and percentage of subjects with virologic failure – Safety set
14.4.5.1	Graphs of individual subject values of viral load (spaghetti plots) – Safety set
14.4.5.2	Graphs of mean viral load change from baseline – Safety set
16.2	SUBJECT DATA LISTINGS
16.2.1	Subjects disposition
16.2.1.1	Discontinued subjects - Included set
16.2.1.2	Subjects disposition and analysis sets - Included set
16.2.1.3	End of study status - Included set
16.2.1.4	Subject visit dates - Included set
16.2.2	Protocol deviations
16.2.2.1	Deviations relating to inclusion/exclusion criteria - Safety set
16.2.2.2	Other deviations – Safety set
16.2.3	Subjects excluded from analysis sets - Included set
16.2.4	Demographic data and baseline characteristics
16.2.4.1	Demographic data and baseline characteristics - Safety set
16.2.4.2	Other baseline characteristics
16.2.4.2.1	HCV genotype – Safety set

16.2.4.2.2	HCV RNA – Safety set
16.2.4.2.3	Serology - Safety set
16.2.4.2.4	Childbearing status – Safety set
16.2.4.2.5	Contraception method – Safety set
16.2.4.2.6	Alcohol consumption – Safety set
16.2.4.2.7	Cirrhosis status – Safety set
16.2.4.2.8	Liver biopsy – Safety set
16.2.4.2.9	Fibroscan – Safety set
16.2.4.2.10	Child-Pugh class assessment (only for compensated cirrhosis cohort) – Safety set
16.2.4.2.11	Hepatocellular carcinoma assessment (only for compensated cirrhosis cohorts) – Safety set
16.2.4.3	Medical and surgical history
16.2.4.3.1	Medical and surgical history (except liver diseases) – Safety set
16.2.4.3.2	Liver diseases – Safety set
16.2.4.4	Previous and concomitant medications
16.2.4.4.1	Previous medications - Safety set
16.2.4.4.2	Concomitant medications - Safety set
16.2.5	Compliance and/or drug concentration data
16.2.5.1	Compliance and dosing data
16.2.5.1.1	IMP administration – Safety set
16.2.5.1.2	Meals intake – Safety set
16.2.5.2	Pharmacokinetic data
16.2.5.2.1	Plasma pharmacokinetic concentrations and parameters
16.2.5.2.1.1	AL-335, ALS-022399 and ALS-022227

16.2.5.2.1.1.1	Plasma concentrations for AL-335, ALS-022399 and ALS-022227 - Pharmacokinetic set
16.2.5.2.1.1.2	Plasma concentrations for AL-335, ALS-022399 and ALS-022227 – Subgroup of subjects who discontinue the study for an adverse event, experience a severe adverse event or a serious adverse event - Pharmacokinetic set
16.2.5.2.1.1.3	Individual plasma concentration time curves for AL-335, ALS-022399 and ALS-022227- Pharmacokinetic set
16.2.5.2.1.1.4	PK parameters in plasma for AL-335, ALS-022399 and ALS-022227 - Pharmacokinetic set
16.2.5.2.1.1.5	PK parameters in plasma for AL-335, ALS-022399 and ALS-022227 – Subgroup of subjects who discontinue the study for an adverse event, experience a severe adverse event or a serious adverse event – Pharmacokinetic set
16.2.5.2.1.2	Simeprevir
16.2.5.2.1.2.1	Plasma concentrations for Simeprevir - Pharmacokinetic set
16.2.5.2.1.2.2	Plasma concentrations for Simeprevir – Subgroup of subjects who discontinue the study for an adverse event, experience a severe adverse event or a serious adverse event - Pharmacokinetic set
16.2.5.2.1.2.3	Individual plasma concentration time curves for Simeprevir - Pharmacokinetic set
16.2.5.2.1.2.4	PK parameters in plasma for Simeprevir - Pharmacokinetic set
16.2.5.2.1.2.5	PK parameters in plasma for Simeprevir – Subgroup of subjects who discontinue the study for an adverse event, experience a severe adverse event or a serious adverse event - Pharmacokinetic set
16.2.5.2.1.3	Odalasvir
16.2.5.2.1.3.1	Plasma concentrations for Odalasvir - Pharmacokinetic set
16.2.5.2.1.3.2	Plasma concentrations for Odalasvir – Subgroup of subjects who discontinue the study for an adverse event, experience a severe adverse event or a serious adverse event - Pharmacokinetic set

16.2.5.2.1.3.3	Individual plasma concentration time curves for Odalasvir - Pharmacokinetic set
16.2.5.2.1.3.4	PK parameters in plasma for Odalasvir - Pharmacokinetic set
16.2.5.2.1.3.5	PK parameters in plasma for Odalasvir – Subgroup of subjects who discontinue the study for an adverse event, experience a severe adverse event or a serious adverse event - Pharmacokinetic set
16.2.6	Efficacy data
16.2.6.1	HCV RNA – Safety set
16.2.6.2	HCV RNA for subjects with virologic failures– Safety set
16.2.7	Adverse event listings
16.2.7.1	All adverse events – Included set
16.2.7.2	Treatment emergent adverse events - Safety set
16.2.7.3	Serious adverse events – Included set
16.2.7.4	Treatment emergent adverse events leading to study drug discontinuation – Safety set
16.2.7.5	Treatment emergent adverse events of special interest - Safety set
16.2.7.6	Adverse events with fatal outcome – Included set
16.2.7.7	Rash assessments
16.2.7.7.1	Photosensitivity – Safety set
16.2.7.7.2	Rash assessments – Safety set
16.2.7.7.3	Associated rash or cutaneous event – Safety set
16.2.7.7.4	Rash or cutaneous event follow-up – Safety set
16.2.7.7.5	Final rash, cutaneous event or photosensitivity evaluation – Safety set
16.2.7.7.6	Primary lesions of rash or cutaneous event – Safety set
16.2.7.7.7	Secondary lesions of rash or cutaneous event – Safety set

16.2.7.7.8	Rash questionnaire – Safety set
16.2.7.7.9	Rash event grading – Safety set
16.2.8	Clinical laboratory data
16.2.8.1	Haematology
16.2.8.1.1	Normal ranges for SI units and local units
16.2.8.1.2	All haematology values (SI unit) - Safety set
16.2.8.2	Blood chemistry
16.2.8.2.1	Normal ranges for SI units and local units
16.2.8.2.2	All blood chemistry values (SI unit) - Safety set
16.2.8.3	Coagulation
16.2.8.3.1	Normal ranges for SI units and local units
16.2.8.3.2	All coagulation values (SI unit) - Safety set
16.2.8.4	Urinalysis
16.2.8.4.1	Normal ranges for SI units and local units
16.2.8.4.2	All urinalysis values (SI unit) - Safety set
16.2.8.5	Hormonology – Safety set
16.2.9	Other safety parameters
16.2.9.1	Vital signs data
16.2.9.1.1	PCSA ranges
16.2.9.1.2	Vital signs parameters - Safety set
16.2.9.2	Electrocardiogram data
16.2.9.2.1	PCSA ranges
16.2.9.2.2.1	Standard 12-lead ECG parameters (centrally read data) - Safety set

16.2.9.3	Echocardiogram data – Safety set
16.2.9.4	Weight and BMI – Safety set
16.2.9.5	Physical examination – Safety set
16.2.9.6	Pregnancy test - Safety set
16.2.9.7	Toxicology – Safety set

#### 11.4 Appendix 4: Events of special/clinical interest

##### 11.4.1 Search terms for Events of Special/Clinical Interest

	MedrDRA Term Level	Searching Terms
Events of special interest		
Cardiac Events	SMQ	Cardiac arrhythmias (SMQ) [Arrhythmia related investigations, signs and symptoms (SMQ); Cardiac arrhythmia terms (incl bradyarrhythmias and tachyarrhythmias) (SMQ)]; Cardiac failure (SMQ); Cardiomyopathy (SMQ); Ischaemic heart disease (SMQ)[ Myocardial infarction (SMQ)]; Shock (SMQ)[ Shock-associated circulatory or cardiac conditions (excl torsade de pointes) (SMQ)]; Torsade de pointes/QT prolongation (SMQ);  Please see Appendix 3
Increased Bilirubin	MedDRA PTs	Bilirubin conjugated abnormal Bilirubin conjugated increased Bilirubin excretion disorder Bilirubinuria Blood bilirubin abnormal Blood bilirubin increased Blood bilirubin unconjugated increased Hyperbilirubinaemia Icterus index increased Jaundice Jaundice cholestatic Jaundice extrahepatic obstructive Jaundice hepatocellular Ocular icterus Urine bilirubin increased Yellow skin
Events of clinical interest		
Rash (all type)	MedDRA HLT, PTs	Erythemas - HLT Papulosquamous conditions - HLT Rashes, eruptions and exanthems NEC - HLT PT: Photodermatosis

		Photosensitivity reaction Polymorphic light eruption Solar dermatitis Sunburn
	SMQ	SMQ-Severe cutaneous adverse reaction: All narrow terms and selected broad terms (refer APPENDIX 2B below)
Pruritus	MedDRA HLT	Pruritus NEC
Photosensitivity conditions	MedDRA PTs	Photodermatosis Photosensitivity reaction Polymorphic light eruption Solar dermatitis Sunburn

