4.7.1 Study Treatment Stopping Criteria

The occurrence of any one of the following treatment emergent events in any ongoing study using ODV at therapeutic doses:

- 2nd degree Mobitz Type 2 or 3rd degree heart block;
- drop in ejection fraction (EF) by ≥ 10 points with absolute EF $< 50\%$;
- a cardiac event that is serious, severe or life-threatening;

will lead to stop of recruitment and dosing in all subjects in the current study if adjudicated by the Sponsor, in consultation with the Investigator, to be at least possibly related to the study regimen. Such event(s) will be reported to the Sponsor medical monitor within 24 hours. Upon this notification, a safety assessment of the event by the Sponsor in consultation with the Investigator will take place within 72 hrs and the outcome of the assessment and its associated action towards the study will be reported to Health Authorities and Ethics Committees in compliance with safety reporting regulations, as applicable.

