The *Division of AIDS (DAIDS) Table for Grading the Severity of Adult and Pediatric Adverse Events, Version 2.0* consists of parameters, or AEs, with severity grading guidance that are to be used in DAIDS clinical trials for safety data reporting to maintain accuracy and consistency in the evaluation of AEs. The term “severe” is not the same as the term “serious” in classifying AEs. The severity of a specific event describes its intensity, and it is the intensity which is graded. Seriousness, which is not graded, relates to an outcome of an AE and is a regulatory definition.

Clinical sites are encouraged to report parameters in the DAIDS AE grading table as they are written to maintain data consistency across clinical trials. However, since some parameters can be reported with more specificity, clinical sites are encouraged to report parameters that convey additional clinical information. For example, diarrhea could be reported as neonatal diarrhea; seizures, as febrile seizures; and pain, as jaw pain.

The DAIDS AE grading table provides an AE severity grading scale ranging from grades 1 to 5 with descriptions for each AE based on the following general guidelines:

- Grade 1 indicates a mild event
- Grade 2 indicates a moderate event
- Grade 3 indicates a severe event
- Grade 4 indicates a potentially life-threatening event
- Grade 5 indicates death (*Note: This grade is not specifically listed on each page of the grading table*).

Other points to consider include:

- Use parameters defined by age and sex values as applicable.
- Male and female sex are defined as sex at birth.
- Unless noted, laboratory values are for term neonates. Preterm neonates should be assessed using local laboratory normal ranges.
- Where applicable, Standard International (SI) units are included in italics.

Selecting and Reporting a Primary AE Term

When selecting a primary AE term to report, sites should select the term that best describes what occurred to the participant. For example, a participant may present with itching, urticaria, flushing, angioedema of the face, and dyspnea. If the underlying diagnosis is determined to be an acute allergic reaction, sites should report “Acute Allergic Reaction” as the primary AE term.

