NOTE: Laboratory abnormalities may have their grading defined in the DAIDs table below, however, all laboratory abnormalities do not necessarily represent an adverse event. If a laboratory abnormality is considered an AE, the AE need not have the same grade as the laboratory abnormality itself. The AE grade for a laboratory abnormality should be defined by the table above.

Major Clinical Conditions

Cardiovascular

PARAMETER	GRADE 1 MILD	GRADE 2 MODERATE	GRADE 3 SEVERE	GRADE 4 POTENTIALLY LIFE- THREATENING
Arrhythmia (by ECG or physical examination) Specify type, if applicable	No symptoms AND No intervention indicated	No symptoms AND Non-urgent intervention indicated	Non-life-threatening symptoms AND Non-urgent intervention indicated	Life-threatening arrhythmia OR Urgent intervention indicated
Blood Pressure Abnormalities¹ Hypertension (with the lowest reading taken after repeat testing during a visit) ≥ 18 years of age	140 to < 160 mmHg systolic OR 90 to < 100 mmHg diastolic	≥ 160 to < 180 mmHg systolic OR ≥ 100 to < 110 mmHg diastolic	≥ 180 mmHg systolic OR ≥ 110 mmHg diastolic	Life-threatening consequences in a participant not previously diagnosed with hypertension (e.g., malignant hypertension) OR Hospitalization indicated
< 18 years of age	> 120/80 mmHg	≥ 95 th to < 99 th percentile + 5 mmHg adjusted for age, height, and gender (systolic and/or diastolic)	≥ 99 th percentile + 5 mmHg adjusted for age, height, and gender (systolic and/or diastolic)	Life-threatening consequences in a participant not previously diagnosed with hypertension (e.g., malignant hypertension) OR Hospitalization indicated
Hypotension	No symptoms	Symptoms corrected with oral fluid replacement	Symptoms AND IV fluids indicated	Shock requiring use of vasopressors or mechanical assistance to maintain blood pressure
Cardiac Ischemia or Infarction Report only one.	NA	NA	New symptoms with ischemia (stable angina) OR New testing consistent with ischemia	Unstable angina OR Acute myocardial infarction

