				Broad	Myocarditis mycotic
				Broad	Myocarditis post infection
				Broad	Myocarditis septic
				Broad	Myocarditis syphilitic
				Broad	Myocarditis toxoplasmal
				Broad	Myoglobinaemia
				Broad	Myoglobinuria
				Broad	Nocturia
				Broad	Nuclear magnetic resonance imaging thoracic abnormal
				Broad	Oedema
				Broad	Orthostatic hypotension
				Broad	Palpitations
				Broad	Papillary muscle disorder
				Broad	Papillary muscle haemorrhage
				Broad	Radiation myocarditis
				Broad	Right atrial dilatation

				Broad	Right atrial enlargement
				Broad	Right atrial pressure increased
				Broad	Right ventricle outflow tract obstruction
				Broad	Right ventricular dilatation
				Broad	Right ventricular enlargement
				Broad	Right ventricular heave
				Broad	Right ventricular systolic pressure decreased
				Broad	Scan myocardial perfusion abnormal
				Broad	Sudden cardiac death
				Broad	Sudden death
				Broad	Surgical ventricular restoration
				Broad	Syncope
				Broad	Systolic anterior motion of mitral valve
				Broad	Systolic dysfunction
				Broad	Ultrasound Doppler abnormal
				Broad	Vascular resistance pulmonary increased
				Broad	Ventricular arrhythmia
				Broad	Ventricular assist device insertion
				Broad	Ventricular dysfunction
				Broad	Ventricular dyskinesia
				Broad	Ventricular dyssynchrony
				Broad	Ventricular hyperkinesia
				Broad	Ventricular hypertrophy
				Broad	Ventricular hypokinesia
				Broad	Ventricular remodelling
				Broad	Viral myocarditis
Ischaemic heart disease (SMQ)					
Myocardial infarction (SMQ)					
				Narrow	Acute coronary syndrome
				Narrow	Acute myocardial infarction
				Narrow	Angina unstable
				Narrow	Blood creatine phosphokinase MB abnormal
				Narrow	Blood creatine phosphokinase MB increased
				Narrow	Coronary artery embolism
				Narrow	Coronary artery occlusion
				Narrow	Coronary artery reocclusion
				Narrow	Coronary artery thrombosis
				Narrow	Coronary bypass thrombosis
				Narrow	Coronary vascular graft occlusion
				Narrow	Kounis syndrome

			Narrow	Myocardial infarction
			Narrow	Myocardial necrosis
			Narrow	Myocardial reperfusion injury
			Narrow	Myocardial stunning
			Narrow	Papillary muscle infarction
			Narrow	Post procedural myocardial infarction
			Narrow	Postinfarction angina
			Narrow	Silent myocardial infarction
			Narrow	Troponin I increased
			Narrow	Troponin increased
			Narrow	Troponin T increased
			Broad	Blood creatine phosphokinase abnormal

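### The cardiac special-interest list has no preferred term for stable angina or myocardial ischaemia, so events coded to those diagnoses drop out of the cardiac special-interest outputs

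*SAP*

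**What the plan says.** SAP 8.1 names cardiac events as a TEAE of special interest and refers to Appendix 4 for the search terms. In 11.4.1 the ischaemic component is "Ischaemic heart disease (SMQ)[ Myocardial infarction (SMQ". In 11.4.3 the infarction heading is the only one expanded under Ischaemic heart disease. The angina terms printed there are "Angina unstable" and "Postinfarction angina".

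The outputs in SAP 8.1 that rest on this list are the special-interest summary table, incidence by toxicity grade and by relationship, time to first occurrence with Kaplan-Meier curves, 2-week incidence and prevalence, and the bar graph of worst grade of cardiac events.

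The protocol's grading table (Appendix F, Cardiovascular) has one row for cardiac ischaemia or infarction. Grades 1 and 2 are not applicable. Grade 3 is "New symptoms with ischemia (stable angina") or new testing consistent with ischaemia. Grade 4 is unstable angina or acute infarction. The instructions to that table state: "Grade 3 indicates a severe event".

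**The concern.** The protocol treats ischaemia and infarction as one graded parameter, but the SAP's cardiac definition holds diagnosis terms for only part of it. The Grade 4 conditions in the row have listed terms. The Grade 3 diagnosis, new stable angina or ischaemia, does not.

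Safety is the primary objective, and protocol 1.3 names the heart as a target organ of odalasvir toxicity. The cardiac special-interest outputs are where a reader will look for a summary of cardiac events by cohort. If a diagnosed ischaemic event falls outside them, whether it is counted depends on the term under which it was recorded and coded.

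**Working it through.** No power or sample-size figure is involved. The check is a reading of the printed list against the grading table.

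**1. What the bracket means.** For arrhythmias, 11.4.1 writes "Cardiac arrhythmias (SMQ) [Arrhythmia related investigations, signs and symptoms (SMQ); Cardiac arrhythmia terms (incl bradyarrhythmias and tachyarrhythmias) (SMQ"), and 11.4.3 expands both bracketed sub-SMQs. So the bracket names the branches that are taken. For Ischaemic heart disease one branch is named and one is expanded. No terms stand directly under the parent heading.

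**2. Count of the infarction block in 11.4.3.** 23 narrow + 15 broad = 38 preferred terms. Two contain the word angina (the unstable and post-infarction terms). None is a term for stable angina, angina pectoris or myocardial ischaemia.

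**3. The other cardiac headings** (arrhythmias, cardiac failure, cardiomyopathy, shock, torsade/QT). Matching diagnosis terms: 0. The nearest is *Ischaemic cardiomyopathy*, a different condition.

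**4. Grading row against list.**

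| Appendix F row | Grade | Diagnosis term in 11.4.3 |
|---|---|---|
| Acute myocardial infarction | 4 | Yes |
| Unstable angina | 4 | Yes |
| New stable angina / new ischaemia | 3 | None |

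**5. Which term a site would record.** The list includes *Chest pain* and *Dyspnoea* (broad, under Cardiomyopathy). Protocol 7.2.2 prefers the cause of an abnormal finding to the finding itself, and the Appendix F instructions ask sites to report the underlying diagnosis as the primary term. A site that follows them would record angina or ischaemia. Unexplained chest pain is therefore counted as a cardiac event of special interest, while the same episode, once diagnosed as stable angina, is not.

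**6. Illustrative size.** The documents give no ischaemia rate, so one event in a cohort of 20 (the upper planned cohort size) is an assumption. The SAP plans Clopper-Pearson intervals only for virologic response; the same method is used here as a yardstick.

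- Counted: 1/20 = 5%, 95% CI 0.1% to 24.9%.
- Dropped: 0/20 = 0%, upper limit 1 − 0.025^(1/20) = 16.8%.

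In a cohort of 10, the lower planned size, the point estimate would move from 1/10 = 10% to 0%. Because the row starts at Grade 3, the worst-grade bar graph would lose an event of at least that grade.

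**The case against.** **Neighbouring terms are listed.** The list holds *Electrocardiogram ST segment abnormal*, *Electrocardiogram repolarisation abnormality*, *Electrocardiogram change*, *Scan myocardial perfusion abnormal* and the troponin and CK-MB terms. A reader might infer that ST depression, T-wave change or positive ischaemia testing cannot be captured. The documents do not support that; much of it can be. This stands, and it confines the gap to the diagnosis terms.

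**The event is still reported.** It would appear in TEAEs by SOC and preferred term, TEAEs by intensity, the Grade 3/4 TEAE summary in SAP 8.1 and listing 14.3.2.2. ECG, echocardiogram and laboratory analyses do not use the list at all. This stands: the event is lost only from the special-interest outputs.

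**The stopping rule.** Protocol 4.7.1 names "a cardiac event that is serious, severe or life-threatening" as a trigger if judged at least possibly related. A reader might infer that the gap weakens this protection. It does not: 4.7.1 works on reported events adjudicated by the sponsor with the investigator, and does not refer to the SAP list. Nor does any document require the list to mirror 4.7.1 or Appendix F.

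**The documented cardiac signal is different.** Protocol 1.3.1 and 1.3.2 describe conduction, QRS/QT and ventricular findings, and 7.5.2 concerns mitochondrial toxicity. All of these are well covered. That is fair and lowers the likely number of affected events. However, the SAP itself includes ischaemic disease in its cardiac definition, and protocol 7.5.1 calls for assessment of cardiac ischaemic injury when CK-MB or troponin rises with CK. Ischaemia is therefore within scope, and the SAP gives no reason for stopping at infarction.

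**Wider extensions.** A reader might want *Hypotension* added on the same logic. The Appendix F instruction "Clinical sites are encouraged to report parameters in the DAIDS AE grading table as they are written" only encourages, *Orthostatic hypotension* is already listed, measured blood pressure is analysed directly, and whether hypotension is a cardiac event is a matter of preference. Mapping every cardiovascular row of Appendix F would bring in haemorrhage and thrombosis, which need not be cardiac.

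**Conclusion.** The gap is real and narrow. The printed list has no diagnosis term for stable angina or myocardial ischaemia, so an event coded to either is absent from every cardiac special-interest output. The number affected is unknown and probably small; in a cohort of 10 to 20, one event decides between 5–10% and 0%.

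The conclusion rests on two assumptions: that the programming follows 11.4.3 as printed, and that coding goes to the diagnosis and not to a listed symptom or test finding. It does not rest on knowledge of what else the parent SMQ contains, which the documents do not give.

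A correction is worth making because the output serves the primary objective and the change is small. It is not evidence that severe ischaemic events would go unreported.

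**What to change.** Add the diagnosis terms for stable angina (angina pectoris) and myocardial ischaemia to the cardiac definition in SAP 11.4.1 and to the term list in 11.4.3, with names confirmed in MedDRA 19.1, the version the SAP uses. Optionally add specific ST-depression and T-wave terms, to match the ST-elevation and U-wave terms already listed. If the restriction to infarction is deliberate, say so and give the reason.

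The cost is a few lines in Appendix 4 and a slightly wider programming flag; no new data or tables are needed. The downside is that a few coronary events unrelated to study drug may enter the cardiac tables. Exclusion 3, which bars angina and coronary heart disease at entry, limits that.
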